6 STUDY ASSESSMENTS AND PROCEDURES

6.1 Time and Events Schedule

If a subject chooses to be removed from the study, withdraws informed consent, or if therapy must be stopped in the interest of the patient's safety, data collected to that point of the study will be collected for intent-to-treat analysis. We will document the reason for a patient's early withdrawal from the study, or the discontinuation of treatment for a patient by the patient's physician or study coordinator.

After the 30-day post-operative physician examination, there will be no further patient assessments. Analysis of all outcomes will be done by EMR analysis, except for treatment compliance as noted above.

Time and Events Schedule for Protocol: CV185-505

Procedure	Prior to Surgery (day of surgery, or <30 days prior)	After Diagnosis of AFib	Upon Hospital Discharge	At Each Anticoagulation Clinic Visit (warfarin)	At 30-Day Post-Operative Examination	After 30-Day Post-Operative Examination
Eligibility Assessments						
Informed Consent		X				
Medical History		X				
Inclusion/Exclusion Criteria		X				
Clinical Drug Supplies						
Randomize		X				
Dispense Study Treatment			X			
Patient Medication Consultation			X			
Safety Assessments						
Pregnancy Test for WOCBP	X					
Renal Function Test	X	X				
Hepatic Function Test		X				
INR measurement	X	X		X		
Monitoring for Bleeding Events			X	X	X	
Monitoring for Thrombotic Events			X	X	X	
Efficacy Assessments						
Measure Apixaban Adherence					X	
EMR Analysis of All Other Outcomes						X
Outcomes Statistical Analysis						X

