Study Objectives:	
1) Primary endpoint: freedom from stroke or thromboembolic event will be captured.
 
2) Secondary endpoints: -units of blood given after initiation of anticoagulation medication -total post-operative length of stay -duration from diagnosis of post-operative atrial fibrillation (POAF) to discharge from hospital -time in therapeutic range of INR if on warfarin -patient compliance percentage to apixaban if on apixaban
 
3) Safety assessments: major and minor bleeding events, as defined by the International Society on Thrombosis and Haemostasis, will be captured. Clinical events and blood product utilization will be identified and captured.

Study Design:	
In this open-label, prospective, randomized pilot study, patients who develop atrial fibrillation after isolated coronary artery bypass grafting surgery will be identified. Patients with persistent atrial fibrillation (>12 hours) or recurrent sustained atrial fibrillation (≥ 2 episodes of atrial fibrillation lasting longer than 30 minutes) will be candidates for inclusion. Upon meeting study inclusion and exclusion criteria, and after informed consent, patients will be randomized to either the standard of care (warfarin per protocol) or apixaban arms of the trial. Routine postoperative care after CABG will occur in both groups. Upon discharge, anticoagulation in both groups will be managed by the anticoagulation clinic. Patients will be followed for 30 days after surgery.

Accrual Goal: (Total number of subjects)	56 patients
Accrual Rate: (Number of subjects expected per month)	We anticipate enrolling 2-3 patients per month based on current projections.
FPFV: LPFV: Follow Up: (mm/dd/yy)	FPFV: 9/1/16 LPFV: 12/31/18 Follow up: 30 days per patient Final Report: 3/31/19

Correlative Studies: (PK/PD, etc.)
	
Retrospective analysis conducted at our facility:
 
Anderson E, Johnke K, Leedahl D, Dyke, C. Novel oral anticoagulants vs warfarin for the management of postoperative atrial fibrillation: clinical outcomes and cost analysis. American Journal of Surgery. Volume 210, Issue 6, 1095-1103²

Inclusion Criteria:
	
Patients diagnosed with new-onset persistent or recurrent atrial fibrillation after isolated CABG surgery. Persistent atrial fibrillation is defined as an episode of >12 hours. Recurrent atrial fibrillation is defined as 2 or more episodes of atrial fibrillation lasting longer than 30 minutes.

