
Data Analysis Plan
	
Efficacy and safety data will retrospectively assessed and analyzed after the patient has completed the 30-day course of therapy. Events relating to thromboembolism or stroke will be adjudicated using pre-defined endpoint definitions by independent committee members that remain blinded to treatment arm. Safety events, including major bleeding will be as defined by the International Society on Thrombosis and Haemostasis.³ In the hospital, bleeding will be assessed daily by monitoring hemoglobin and the need for transfusions, and defined by a drop in hemoglobin of > 2 gm/dL in the previous 24 hours, or transfusion of at least two units of blood products. After discharge, we will monitor for readmissions related to bleeding, indicated by the need of transfusion of at least two units of blood products.

Statistics:
	
Continuous variables will be expressed as mean ± standard deviation or median with interquartile range (IQR) as appropriate. Continuous variables will be compared using t-tests for parametric data or Wilcoxon analysis for nonparametric data. We will complete the analysis in an intent-to-treat manner. We will include analysis for confidence intervals and other appropriate statistical tests to assess binary outcomes. We realize that statistical comparison between groups will be of limited utility in this pilot study as this study is not powered for comparison of events between groups. Data will be analyzed using JMP software, version 12.0.0 (Cary, NC).

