4.2.4 Discontinuation of Subjects from Treatment

Subjects MUST discontinue investigational product (and non-investigational product at the discretion of the investigator) for any of the following reasons:

- Withdrawal of informed consent (subject's decision to withdraw for any reason).
- Any clinical adverse event, laboratory abnormality, or intercurrent illness which, in the opinion of the investigator, indicates that continued participation in the study is not in the best interest of the subject.
- Pregnancy
 - Instruct WOCBP to contact the investigator or study staff immediately if they suspect they might be pregnant (eg, missed or late menstrual period) at any time during study participation. Institutional policy and local regulations should determine the frequency of on-study pregnancy tests for WOCBP enrolled in the study.
 - The investigator must immediately notify BMS if a study subject becomes pregnant.

- Loss of ability to freely provide consent through imprisonment or involuntary incarceration for treatment of either a psychiatric or physical (eg, infectious disease) illness.
- While patients may request withdrawal from the study at any time, they will be advised to check with their medical provider before discontinuing any anticoagulant medication, for their safety.
- Subjects can voluntarily withdraw from the study at any time, but the investigators will continue to follow the patient so that an intent-to-treat analysis can be performed. Failure to take study medication as prescribed, or failure to follow up as directed with the anticoagulation clinic, will be noted in our analysis to the best extent we are able.
- Any data collected before withdrawal will be used for study outcomes, although it will be noted that the participant did not complete the 30-day course of therapy. Attempts will be made to determine and note the reason for withdrawal.
- All subjects who discontinue should comply with protocol-specified follow-up procedures outlined in Section 6. The only exception to this requirement is when a subject withdraws consent for all study procedures or loses the ability to consent freely (ie, is imprisoned or involuntarily incarcerated for the treatment of either a psychiatric or physical illness). If a subject withdraws before completing the study, the reason for withdrawal must be documented appropriately.

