5.4 Selection and Timing of Dose for Each Subject

Apixaban: Apixaban is to be dosed at 5 mg by mouth twice daily, except in the case of the criteria listed below in “dose modifications”. The duration of therapy will be at least 30 days. The patient’s physician may determine that anticoagulation therapy should be continued after the study period, based on their examination of the patient at the 30-day post-operative examination.

Apixaban should not be used if a patient has active pathological bleeding.

If a dose of apixaban is not taken at the scheduled time, the dose should be taken as soon as possible on the same day and then continue with twice daily administration as before. The dose should not be doubled to make up for a missed dose.

Apixaban can be taken with or without food.

Apixaban is not recommended in patients with severe hepatic impairment. No dose adjustment is recommended for patients with renal impairment alone, including those with end-stage renal disease (ESRD) maintained on hemodialysis, except nonvalvular atrial fibrillation patients who meet the criteria for dosage adjustment. Patients with ESRD (CrCl <15 mL/min) receiving or not receiving hemodialysis were not studied in clinical efficacy and safety studies with ELIQUIS; therefore, the dosing recommendations are based on pharmacokinetic and pharmacodynamic (anti-Factor Xa activity) data in subjects with ESRD maintained on dialysis.

Warfarin: While patients are hospitalized, warfarin will be dosed daily, with daily INR monitoring per hospital protocol. Daily doses may vary from 0.5mg to 15mg by mouth, as determined by patient specific factors such as patient size, hepatic function, INR, concomitant medications, diet, or other factors. Based on these factors or others not listed, there may also be days in which the patient is prescribed to not get does not receive a dose of warfarin.

After discharge from the hospital, warfarin dosing will be subsequently managed by an anticoagulation clinic, per established protocols. All patients will have a goal INR of 2-3 during the duration of the study. The duration of therapy will be at least 30 days. The patient's physician may determine that anticoagulation therapy should be continued after the study period, based on their examination of the patient at the 30-day post-operative examination.

Warfarin should not be used if a patient has active pathological bleeding.

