5.4.1 Dose Modifications

Apixaban: in patients with at least 2 of the following characteristics, age ≥ 80 years, body weight ≤ 60 kg, or serum creatinine ≥ 1.5 mg/dL (133 $\mu\text{mol/L}$), the recommended dose of apixaban is 2.5 mg twice daily.

Warfarin: doses of warfarin will be determined on a daily basis while the patient is in the hospital. After discharge from the hospital, after each INR check, a pharmacist or nurse will contact the patient to communicate the appropriate dosing.

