5.7 Treatment Compliance

Patient compliance will be monitored during the study. While the patient is hospitalized, we will monitor whether apixaban or warfarin is given as directed by the study coordinator. After the patient has been discharged from the hospital, apixaban compliance will be measured by asking the patient to bring any unused medication to their 30-day post-operative appointment, where remaining tablets will be counted. As 60 tablets will be dispensed to each patient (30-day supply), we use the following formula:

$$[(60 - (\text{\# of remaining tablets})) * 100] / [2 * (\text{days since filled})] = \text{percent compliance.}$$

After hospital discharge, warfarin compliance will be monitored by measuring the time in therapeutic INR range (2-3).

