6.3 Safety Assessments

1) Major bleeding, as defined by the International Society on Thrombosis and Haemostasis based on the following criterion:

- a. Fatal bleeding, and/or
- b. Symptomatic bleeding that occurs in a critical area or organ, such as intracranial, intraspinal, intraocular, retroperitoneal, pericardial, in a non-operated joint, or intramuscular with compartment syndrome, assessed in consultation with the surgeon, and/or
- c. Extrasurgical site bleeding causing a fall in hemoglobin level of 20 g/L (2g/dL) or more, or leading to transfusion of two or more units of whole blood or red cells within 24-48 hours of the bleeding and/or
- d. Surgical site bleeding that requires a second intervention – open, arthroscopic, endovascular- or a hemarthrosis of sufficient size as to interfere with rehabilitation by delaying mobilization or delayed wound healing, resulting in prolonged hospitalization or a deep wound infection, and/or
- e. Unexpected surgical site bleeding, prolonged and/or sufficiently large to cause hemodynamic instability, as assessed by the surgeon, with a fall in hemoglobin of at least 20 g/L (2g/dL) or transfusion of two or more units of whole blood or red cells within 24 hours of the bleeding.³

2) Clinical relevant non-major bleed, defined as any notable bleeding not classified as major.

3) Pregnancy tests will be performed pre-operatively on the day of surgery for all WOCBP, via urine hCG screening.

4) A baseline renal function panel will be obtained either pre-operatively or within 30 days of surgery. The renal function panel includes: glucose, BUN, creatinine, BUN/creatinine ratio, sodium, potassium, bicarbonate, chloride, calcium, phosphorus, albumin, and anion gap.

5) The hepatic function test panel will be ordered before initiating warfarin (if a recent baseline is not available). This panel includes: total protein, albumin, alk phos, AST, ALT, total bilirubin, direct bilirubin, and indirect bilirubin.

6) INR will be checked before surgery to ensure the patient's INR is within normal limits in preparation for their surgery, regardless of whether they were previously on warfarin, and again upon initiation of warfarin therapy. INR will be checked daily in the hospital, and at each visit to the anticoagulation clinic. These visits are usually scheduled within three days of discharge from the hospital, then twice weekly until the INR is therapeutic, then weekly for the duration of the study.

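### Bleeding and thrombosis monitoring between discharge and the 30-day exam is scheduled only at warfarin-labelled visits, and bleeds other than haemorrhagic stroke get no blinded classification

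*Combined protocol and SAP*

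**What the plan says.** **Clinic contact.** The Section 6.1 table marks bleeding and thrombosis monitoring at discharge, at the 30-day exam, and in one column between them, headed "At Each Anticoagulation Clinic Visit (warfarin". The synopsis (Study Design) states: "Upon discharge, anticoagulation in both groups will be managed by the anticoagulation clinic". Section 4.2.4 names no arm when it says that "failure to follow up as directed with the anticoagulation clinic, will be noted in our analysis". Section 5.4 describes clinic management for one drug: "After discharge from the hospital, warfarin dosing will be subsequently managed by an anticoagulation clinic, per established protocols". Under warfarin, Section 5.4.1 adds that "after each INR check, a pharmacist or nurse will contact the patient to communicate the appropriate dosing". Both are silent on clinic contact for apixaban. The only visit frequency is in the INR item of Section 6.3: "These visits are usually scheduled within three days of discharge from the hospital, then twice weekly until the INR is therapeutic, then weekly". The only apixaban-specific check after discharge is in Section 5.7: "apixaban compliance will be measured by asking the patient to bring any unused medication to their 30-day post-operative appointment".

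**What counts after discharge.** The synopsis (Data Analysis Plan) states: "After discharge, we will monitor for readmissions related to bleeding, indicated by the need of transfusion of at least two units of blood products". Section 4.1 repeats this and adds no study phone calls. Section 2.1 lists major and minor bleeding to postoperative day 30 as an objective.

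**Classification.** Section 5.5 says that the study is unblinded. Blinded independent adjudication appears in the synopsis, Section 4.1 and Section 6.4.1, each time for thromboembolism or stroke only. Section 6.4.1 counts haemorrhagic stroke among the strokes. Section 6.3 gives the surgeon a role in two major-bleeding criteria and defines the clinically relevant non-major category as whatever bleeding is notable but not major, with no named classifier.

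**The concern.** Section 6.1 takes every outcome except compliance from the electronic record. A bleed that causes no readmission is found there only if someone asked about it or saw it and wrote it down. If one arm is seen several times between discharge and the 30-day exam and the other is not, the arms can differ in recorded non-major bleeding even when their true rates are equal. Intent-to-treat analysis does not correct unequal detection.

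Classification is a separate matter. Whether a bleed is notable is a judgement. Here nothing stops it being made by someone who knows the treatment, in hospital as well as after discharge.

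At stake is the safety signal that Section 1.2 hopes for and that Section 9.1 offers as a reference for later studies. Thrombosis shares the same schedule columns, but those events are physician-diagnosed and adjudicated blind, so the concern is chiefly about bleeding.

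**Working it through.** The plan states no figure on this point, so there is none to reproduce. The check sets the sections side by side and counts scheduled contacts.

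**1. Who is seen between discharge and the 30-day exam?**
- Both arms: synopsis (explicit) and Section 4.2.4 (no arm named).
- Warfarin only: the Section 6.1 column label. Sections 5.4, 5.4.1 and 6.3 fit that label, since they describe clinic contact only around warfarin dosing and INR.
- The same column holds the INR row, so the label may have been meant for that row alone. The text does not settle this.

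**2. How many monitored visits does the literal schedule imply?** From Section 6.3: a first visit within three days of discharge, then twice weekly (taken as every 3.5 days) until the INR is therapeutic, then weekly. Assumed, because the documents do not say: discharge on postoperative day 5 to 8, first visit 1 to 3 days later, and w = 0, 1 or 2 weeks to a therapeutic INR. With the first visit on day F and visits counted before day 30:

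visits = (30 − F)/7 rounded up, plus w

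| F | (30 − F)/7 rounded up | w = 0 | w = 1 | w = 2 |
|---|---|---|---|---|
| 6 to 8 | 4 | 4 | 5 | 6 |
| 9 to 11 | 3 | 3 | 4 | 5 |

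A warfarin patient therefore has 3 to 6 monitored visits. Discharge on day 10 gives 3 to 5, inside the same range. An apixaban patient has 0 under the literal label. If the synopsis is followed with similar contact in both arms, the gap is 0.

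**3. Which bleeds count after discharge?** If the readmission-and-transfusion rule defines capture, post-discharge minor bleeds count in neither arm. That removes the imbalance but contradicts Section 2.1. If Section 2.1 governs, minor bleeds count, and unequal contact can matter.

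**4. What does one patient weigh?** Section 4.1 plans 28 per arm. Each patient whose bleed is recorded in one arm but would be missed in the other moves the observed difference by 1/28 = 3.6 percentage points. The number of such patients is unknown.

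**5. Which bleeds are classified blind?** Haemorrhagic stroke is, as part of the primary assessment. No section extends blinded review to any other bleed. Most major criteria rest on death, haemoglobin fall, transfusion or re-intervention, which limits the room for judgement. The non-major category has no such anchor.

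**The case against.** The strongest reply is that an apixaban patient has no labelled clinic visits but still has several routes of capture. Section 7 collects serious events from consent to 30 days after dosing stops, and non-serious events from the start of study drug. Routine postoperative calls continue, the 30-day exam monitors both arms, and the record review covers everyone. This stands. It confines the concern to non-major bleeds that cause no readmission. It also rules out a reading that the schedule might suggest, that apixaban patients go unmonitored after discharge.

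The direction is open to challenge too. Section 7 ties adverse events to the investigational product, which Section 5.1 says is apixaban, while Section 4.2.1 uses the term study drug for both treatments. If event collection were run more closely on apixaban, the imbalance could shrink or reverse. The direction given here therefore follows from the literal schedule only.

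On classification, a reader might infer that no bleed at all is judged blind. Section 6.4.1 contradicts that for haemorrhagic stroke. The surgeon's view of haemodynamic instability also cannot create a major bleed alone, because the criterion requires a haemoglobin fall or transfusion as well.

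Finally, the plan says that it is not powered to compare events. That is true and limits what is at stake, but unequal detection is a matter of bias, which small numbers do not excuse.

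**Conclusion.** The concern holds in a limited form. The plan contradicts itself on clinic contact by arm and on whether post-discharge non-major bleeds count. If the schedule is followed literally and those bleeds do count, they are more likely to be recorded on warfarin, with 3 to 6 monitored visits against none under the assumed discharge day and time to therapeutic INR.

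A reader might go further and conclude that the bleeding comparison is biased towards apixaban by some definite amount. The documents do not support that. They give no detection rates, the label may be a slip, and the imbalance disappears if the synopsis describes practice or if the readmission rule is applied as written. The bias may be zero.

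The lack of blinded classification holds whichever way the label is read. It matters mainly for the non-major category, in hospital and after discharge. Both gaps should be closed because the remedy is cheap, but neither invalidates the trial.

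**What to change.** 1. Reconcile the synopsis (Study Design) and Sections 4.2.4, 5.4, 5.4.1, 6.1 and 6.3 on what clinic contact each arm has after discharge, and label the schedule column to match. Reconcile the synopsis (Data Analysis Plan) and Section 4.1 with Section 2.1 on whether post-discharge non-major bleeds count.
2. At the existing 30-day exam, ask both arms the same scripted bleeding and thrombosis questions covering the whole period since discharge. Define this as an endpoint assessment, separate from Section 7, which asks for open-ended questioning about adverse events.
3. Have the existing blinded committee classify bleeds that are candidates for the major or clinically relevant non-major category, from summaries with treatment and INR masked.
4. Record which source captured each event and report counts by source and arm descriptively, dropping none.

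The cost is wording changes, a short form, one table, redaction work and committee time. No visits or patients are added. If 20% to 30% of patients bleed (an assumption), the expected number is 56 × 0.20 = 11.2 to 56 × 0.30 = 16.8, or about 11 to 17 patients, with central 95% binomial ranges of 6 to 17 and 10 to 24. The load may be higher, because suspected cases outnumber confirmed ones. Recall over several weeks is imperfect and masking can fail, so bias is reduced, not removed.

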6.2 Study Materials

Bristol-Myers Squibb (BMS) will provide apixaban at no cost for this study.

6.3 Safety Assessments

1) Major bleeding, as defined by the International Society on Thrombosis and Haemostasis based on the following criterion:

- a. Fatal bleeding, and/or
- b. Symptomatic bleeding that occurs in a critical area or organ, such as intracranial, intraspinal, intraocular, retroperitoneal, pericardial, in a non-operated joint, or intramuscular with compartment syndrome, assessed in consultation with the surgeon, and/or
- c. Extrasurgical site bleeding causing a fall in hemoglobin level of 20 g/L (2g/dL) or more, or leading to transfusion of two or more units of whole blood or red cells within 24-48 hours of the bleeding and/or
- d. Surgical site bleeding that requires a second intervention – open, arthroscopic, endovascular- or a hemarthrosis of sufficient size as to interfere with rehabilitation by delaying mobilization or delayed wound healing, resulting in prolonged hospitalization or a deep wound infection, and/or
- e. Unexpected surgical site bleeding, prolonged and/or sufficiently large to cause hemodynamic instability, as assessed by the surgeon, with a fall in hemoglobin of at least 20 g/L (2g/dL) or transfusion of two or more units of whole blood or red cells within 24 hours of the bleeding.³

2) Clinical relevant non-major bleed, defined as any notable bleeding not classified as major.

3) Pregnancy tests will be performed pre-operatively on the day of surgery for all WOCBP, via urine hCG screening.

4) A baseline renal function panel will be obtained either pre-operatively or within 30 days of surgery. The renal function panel includes: glucose, BUN, creatinine, BUN/creatinine ratio, sodium, potassium, bicarbonate, chloride, calcium, phosphorus, albumin, and anion gap.

5) The hepatic function test panel will be ordered before initiating warfarin (if a recent baseline is not available). This panel includes: total protein, albumin, alk phos, AST, ALT, total bilirubin, direct bilirubin, and indirect bilirubin.

6) INR will be checked before surgery to ensure the patient's INR is within normal limits in preparation for their surgery, regardless of whether they were previously on warfarin, and again upon initiation of warfarin therapy. INR will be checked daily in the hospital, and at each visit to the anticoagulation clinic. These visits are usually scheduled within three days of discharge from the hospital, then twice weekly until the INR is therapeutic, then weekly for the duration of the study.

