
Exclusion Criteria:
	
 1. Patients undergoing valve replacement or with an artificial heart valve, or with moderate or severe mitral stenosis 2. Stroke within the previous 7 days. 3. Patients currently experiencing active bleeding precluding initialization of anticoagulation therapy in the opinion of their managing physician, or with increased bleeding risk (as determined by the attending surgeon) believed to be a contraindication to anticoagulation at the time of randomization. 4. Atrial fibrillation due to a reversible cause other than recent surgery 5. Planned major surgery requiring stoppage of anticoagulation therapy during the trial period. 6. Patients taking warfarin, apixaban, rivaroxaban, dabigatran, edoxaban, or enoxaparin at home for any indication in the 15 days prior to surgery. Patients taking clopidogrel or ticagrelor within 5 days prior to surgery, patients taking prasugrel within 7 days prior to surgery, and patients taking ticlopidine within 10 days prior to surgery. 7. Patients receiving clopidogrel, ticagrelor, prasugrel, or ticlopidine during the study period. 8. Patients diagnosed with persistent atrial fibrillation chronically before undergoing surgery. 9. Patients with paroxysmal atrial fibrillation requiring oral anticoagulation prior to surgery. 10. Severe renal insufficiency (serum creatinine level of >2.5 mg/dL or CrCL<25 ml/min) for consecutive measurements. 11. Patients who are pregnant or of child-bearing age. 12. Patients <18 years of age. 13. Patients unable to give informed consent
-----------------------------------	--

Criteria for Evaluation: (Efficacy, safety, stopping rules, etc.)
	
Efficacy will be measured by the freedom from systemic thromboembolism or stroke during the study period. Events relating to thromboembolism or stroke will be adjudicated using pre-determined definitions by independent committee members that remain blinded to the patient's treatment arm.
 
Safety, including major and minor bleeding will be quantified and defined by the Society on Thrombosis and Haemostasis, as described in section 6.4.2, subsection (2). Clinical events that occur during the study period will be quantified and measured, including adverse events, serious adverse events, blood product utilization, length of stay, duration of atrial fibrillation, and time to adequate anticoagulation.

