- Potential or suspected cases of liver injury including but not limited to liver test abnormalities, jaundice, hepatitis or cholestasis.

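### Severe hepatic impairment is a stated caution for apixaban but not an exclusion, and no text places the liver panel before randomization (low severity)

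*Combined protocol and SAP*

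**What the plan says.** Four parts of the combined protocol and SAP bear on this.

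- **Drug caution (5.4).** "Apixaban is not recommended in patients with severe hepatic impairment". For warfarin, the same section lets the daily dose vary "as determined by patient specific factors such as patient size, hepatic function, INR, concomitant medications, diet, or other factors". The apixaban dose-reduction rule in 5.4.1 uses age, weight and creatinine only.
- **Eligibility (synopsis and 4.2.2).** Neither list names liver disease or a liver-test threshold. The only organ-function exclusion is renal. The closest general rule covers patients "with increased bleeding risk (as determined by the attending surgeon) believed to be a contraindication to anticoagulation at the time of randomization".
- **Timing in the text (6.3 item 5).** "The hepatic function test panel will be ordered before initiating warfarin (if a recent baseline is not available"). Apixaban is not mentioned.
- **Timing in the schedule (6.1).** The row "Hepatic Function Test" has one mark, under the column that follows AFib diagnosis. Consent, medical history, the eligibility check and randomization are marked in the same column.

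**The concern.** The protocol advises against one of its two study drugs in a named condition, but does not use that condition to decide who enters. A patient for whom 5.4 advises against apixaban can therefore meet every written criterion and be assigned to it.

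The consequence differs by arm. A clinician with a warfarin patient can adapt the dose to liver function and stay within the protocol. A clinician with an apixaban patient has no dose rule for the liver. The choice is to give a drug that the protocol advises against or to take the patient off assigned treatment. In the second case the departure occurs in one arm only, while the intent-to-treat analysis (9.3) rightly keeps the patient there. Settling the question before assignment avoids both outcomes and treats the arms alike.

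The wording of 6.3 item 5 has a further effect. A site that follows it literally could start apixaban without a baseline liver panel. Suspected liver injury is an event of special interest under 7.1 ("Potential or suspected cases of liver injury including but not limited to liver test abnormalities, jaundice, hepatitis or cholestasis"), and it is harder to interpret without a baseline.

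**Working it through.** The plan gives no figure to reproduce. The check compares the text and then sizes the gap under assumed rates.

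**1. Do the exclusion lists cover the condition?** The synopsis has 13 numbered exclusions. Section 4.2.2 has 16 non-empty bullets: 3 on target disease, 4 on medical history, 2 on concomitant medication, 1 on laboratory findings, 1 on allergy, 1 on reproductive status and 4 others (3 + 4 + 2 + 1 + 1 + 1 + 4 = 16). None of the 29 entries names the liver.

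**2. Are other cautions turned into exclusions?**

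| Condition | Sections 5.4 and 5.4.1 | Exclusion lists |
|---|---|---|
| Active bleeding | Neither drug to be used | Excluded in both lists |
| Renal impairment | No apixaban dose change for renal impairment alone | Severe insufficiency excluded in both lists |
| Severe hepatic impairment | Apixaban not recommended | Not listed |

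The hepatic caution is the one without a matching exclusion. That looks more like an omission than a choice.

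**3. Does any text put the liver result before randomization?** Section 6.3 item 5 ties the panel to starting warfarin. The arm is known only after randomization, so this rule cannot ensure a result beforehand. The schedule marks the panel for everyone but gives no order within the column. Even if the panel came first, an abnormal result would make nobody ineligible, because no criterion exists.

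**4. How many patients might be affected?** The inputs are n = 28 apixaban patients (section 4.1) and a rate p of severe hepatic impairment among enrolled patients. The documents do not give p, so the rates below are assumptions.

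- Expected number = 28 × p
- Chance of at least one = 1 − (1 − p)^28

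| Assumed p | Expected number | Chance of at least one |
|---|---|---|
| 0.1% | 28 × 0.001 = 0.03 | 1 − 0.999^28 = 2.8% |
| 0.5% | 28 × 0.005 = 0.14 | 1 − 0.995^28 = 13.1% |
| 1% | 28 × 0.01 = 0.28 | 1 − 0.99^28 = 24.5% |

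One such patient would be 1/28 = 3.6% of the arm.

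**The case against.** The strongest reply is that several safeguards already make such a patient unlikely, and that what remains is drafting.

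- **Selection before entry.** Every candidate has been accepted for CABG, and 6.3 item 6 has INR checked against normal limits before surgery, "regardless of whether they were previously on warfarin, and again upon initiation of warfarin therapy". This is a real filter and pulls the likely rate towards the low end of the range. INR is not a complete measure of liver function, though, and no eligibility rule refers to it.
- **Surgeon's judgement.** The bleeding-risk exclusion could catch some of these patients. It is discretionary, does not mention the liver and requires no liver test.
- **Stopping rule.** Section 4.2.4 requires the investigational product to be stopped for a laboratory abnormality or illness when the investigator judges that continuing is against the patient's interest. This limits harm, but it acts after entry and produces the one-arm departure described above.
- **Reading of 5.4.** The sentence sits among labelling-style text that also covers dialysis dosing, which the renal exclusion makes largely irrelevant here. It can be read as a prescriber's caution, and then the protocol does not contradict itself. The caution still has to be acted on somewhere, and before assignment is the only point at which both arms are treated equally.
- **Visit grid.** Schedules seldom give an order within a column, and the renal test sits under the same safety heading although renal function is an exclusion. This is fair: the schedule is not wrong. The gap is the missing criterion and the warfarin-only sentence in 6.3.

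It is also fair that the assumed rates have no source in the documents, and that the 24.5% is simply the top of a chosen range.

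**Conclusion.** The point holds, at low severity. The written eligibility rules admit a patient for whom the protocol advises against one study drug, and no text requires a liver result before randomization. The existing safeguards are discretionary, not specific to the liver, or act after entry. They narrow the gap without closing it.

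The number affected is probably zero or one. That judgement rests on the assumed rates of 0.1% to 1%, which take no account of selection for surgery. The endpoints, the sample size of 56 and the planned analyses are unaffected, and the plan already says that it is not powered to compare events between groups. The case for acting is participant safety, equal handling of the arms and consistency within the protocol.

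**What to change.** 1. Add severe hepatic impairment to the synopsis exclusions and to 4.2.2. The sponsor should set the definition, for example by Child-Pugh class.
2. Reword 6.3 item 5 to agree with the schedule: in both arms, a hepatic panel or a recent baseline is reviewed before randomization.
3. Define how recent the baseline must be. The schedule's pre-surgery column ("Prior to Surgery (day of surgery, or <30 days prior") offers a ready window if the sponsor accepts a pre-operative value. The hepatic row has no mark in that column, so this would be a deliberate choice.

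**Cost.** One line in each list and one reworded sentence. The schedule already has the panel for all patients, so on that reading no test is added. If the site has been following the narrower wording of 6.3, apixaban patients without a recent baseline would need a panel, at most 28 of them. Randomization may occasionally wait a short time for one laboratory result, and a very small number of patients may be newly excluded.
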